1.3 Control-IQ Use in Type 2 Diabetes

- 32 Insulin pump use in individuals with type 2 diabetes is relatively low. However, there is an
- increasing uptake of pump use in this population. The benefits of insulin pump use with
- 34 Automated Insulin Dosing (AID) technology in individuals with type 2 diabetes has not been
- well established in clinical trials, although real-world data have shown that use of Control-IQ can
- 36 produce significant glycemic benefits in this population, whether transitioning from multiple
- daily injections (MDI) or prior pump use. Retrospective analysis of 134 prior pump users with
- 38 type 2 diabetes who purchased a new Tandem insulin pump with Control-IQ technology showed
- 39 time in range was 76% (IQR 69-82%) and time below range was 0.5% (IQR 0.2-1.0%) after 180
- 40 days of use. For 173 participants transitioning from MDI, use of Control-IQ technology resulted
- 41 in time of range 70-180 mg/dL of 74% (IQR 63-83%) and time below 70 mg/dL 0.3% (IQR 0.1-
- 42 0.6%) at 180 days of use (5). Additionally, retrospective analysis of real-world use out to one
- 43 year in 378 individuals with type 2 diabetes who software updated from Basal-IQ technology to
- 44 Control-IQ technology showed significant improvements in time in range 70-180 mg/dL (69% at
- baseline versus 78% at one year) (4). In an analysis of Medicare and Medicaid Control-IQ users,
- 46 500 individuals with type 2 diabetes improved from 64% TIR at baseline to 72% after using
- 47 Control-IQ for at least 30 days (6).
- 48 A prospective single-arm 6-week trial, conducted to provide preliminary data on the safety and
- 49 glycemic outcomes with use of Control-IQ in adults with T2D, showed that use of Control-IQ
- was safe, with no increase in CGM-measured hypoglycemia and a substantial improvement in
- 51 time in range and mean glucose related to a reduction in hyperglycemia (7). Thirty adults with
- 52 T2D (mean age 54±12 years, mean HbA1c 8.6±1.2, median BMI 31) using either MDI (N=15),
- 53 pump (N=2) or basal without bolus insulin (N=13) collected unblinded CGM data (baseline)
- followed by an open-loop period prior to initiating use of CIQ for 6 weeks. Primary outcomes
- were superiority for CGM time >180 mg/dL and non-inferiority for time <54 mg/dL. Mean time
- >180 mg/dL decreased from 44% at baseline to 29% with CIQ, a reduction of 3.6 hours per day
- 57 (P=0.004), mean time 70-180 mg/dL increased from 56% to 71% (P=0.004), and mean glucose

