1.4 Rationale and Objectives

- There are many patients with T2D who are unable to achieve optimal glucose control despite the
- use of intensive insulin therapy often with the concomitant use of other glucose-lowering drugs.
- An AID system such as Control-IQ offers the potential for lower HbA1c levels and increased
- 69 time in range without increasing hypoglycemia and for improved quality of life. In view of the
- 70 promising results from the preliminary study evaluating Control-IQ in T2D, a larger trial with a
- randomized trial design is needed to more broadly and rigorously evaluate the efficacy and safety
- of Control-IQ in adults with T2D using basal-bolus insulin therapy with or without additional
- 73 glucose-lowering medications. Thus, the main objectives of this trial are:

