294 295 296 297	For security and confidentiality purposes, participants will be assigned an identifier that will be used instead of their name. Protected health information gathered for this study will be shared with the coordinating center, the Jaeb Center for Health Research in Tampa, FL. De-identified participant information may also be provided to research sites involved in the study.

1298	Chapter 11: Statistical Considerations
1299	11.1 Statistical and Analytical Plans
1300 1301	The approach to sample size and statistical analyses are summarized below. A detailed Statistical Analysis Plan will be written and finalized prior to the completion of the study.
1302 1303 1304	The primary statistical analyses will involve comparisons of the randomized treatment groups. Additionally, certain single-arm analyses will be conducted on the data collected for the AID group as described in section 11.15.
1305	11.2 Statistical Hypotheses
1306 1307 1308	The primary endpoint for this study is HbA1c at 13-weeks adjusted for baseline HbA1c. The intervention will be considered effective if the AID group is superior to the Control group using a statistical significance of α =0.05.
1309	The null/alternative hypotheses for the primary endpoint are:
1310 1311 1312	 Null Hypothesis: There is no difference in mean HbA1c at 13 weeks between AID and Control Alternative Hypothesis: Mean HbA1c at 13 weeks is different for AID and Control.
1313 1314	Similarly, the null and alternative hypotheses for all of the secondary efficacy endpoints in the hierarchy are:
1315 1316 1317	 Null Hypothesis: There is no difference in the endpoint at 13 weeks between AID and Control Alternative Hypothesis: Endpoint at 13 weeks is different for AID and Control.
1318	11.3 Sample Size
1319 1320 1321 1322	The sample size of 330 randomized participants was selected to provide sufficient exposure to the AID system for regulatory purposes. This equates with a maximum of 220 using the AID system for 13 weeks. Assuming 10% drop out rate in each group, there will be 200 using the system for 13 weeks.

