1323 1324 1325 1326 1327 1328	HbA1c data from N=30 participants in the 2IQ pilot study were used to estimate the SD for the power calculation. The SD for baseline values was 1.0%. Assuming a similar SD at follow-up, correlation of 0.3 with baseline, and a two-sided test with type 1 error at 5%, a sample size of N=300 completers will be able to detect an HbA1c difference as small as 0.38% with 90% power. There will be 85% power to detect a difference of 0.35% and 80% power for a difference of 0.33%.
1329	11.4 Efficacy Outcome Measures
1330	11.4.1 Primary Efficacy Endpoint
1331	• HbA1c at 13 weeks (superiority)

1332	11.4.2 Secondary Efficacy Endpoints Included in Hierarchical Analysis
1333 1334	The following secondary endpoints will be tested for superiority, with a hierarchical testing approach to protect the type 1 error rate as described in section 11.13.
1335	• Time in range 70-180 mg/dL
1336	Mean glucose
1337	• Time $> 180 \text{ mg/dL}$
1338	• Time $>$ 250 mg/dL
1339	• CGM-measured prolonged hyperglycemia events (defined in section 11.7.1)
1340	• Time <70 mg/dL
1341	• Time <54 mg/dL
1342	CGM-measured hypoglycemia events (defined in section 11.7.1)
1343	• Coefficient of variation
1344	
1345	11.4.3 Other Secondary Efficacy Endpoints
1346 1347	The following efficacy endpoints are considered exploratory as they are not included in the overall type 1 error rate. All statistical tests are for superiority.
1348	Binary HbA1c Endpoints:
1349	HbA1c <7.0% at 13 weeks
1350	HbA1c <7.0% at 13 weeks in participants with baseline HbA1c >7.5%
1351	HbA1c <7.5% at 13 weeks
1352	HbA1c improvement from baseline to 13 weeks >0.5%
1353	HbA1c improvement from baseline to 13 weeks >1.0%
1354	HbA1c relative improvement from baseline to 13 weeks >10%
1355	HbA1c improvement from baseline to 13 weeks >1.0% or HbA1c <7.0% at 13 weeks
1356	Continuous CGM-Measured Endpoints:
1357	Time in range 70-140 mg/dL
1358	Area over the curve (70 mg/dL)
1359	Low blood glucose index
1360	Time $>$ 300 mg/dL
1361	Area under the curve (180 mg/dL)
1362	High blood glucose index
1363	Binary CGM-Measure Endpoints
1364	Time in range 70-180 mg/dL $>$ 70%
1365	Time in range 70-180 mg/dL improvement from baseline to 13 weeks ≥5%

1366	Time in range 70-180 mg/dL improvement from baseline to 13 weeks \geq 10%
1367	Time $<$ 70 mg/dL $<$ 4%
1368	Time <54 mg/dL $<1\%$
1369	Time in range 70-180 mg/dL $>$ 70% and time $<$ 54 mg/dL $<$ 1%
1370	Other Endpoints (analyzed for superiority as continuous variables):

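### The power statement uses a pilot HbA1c SD of 1.0%, but Protocol 1.3 gives ±1.2 for what appears to be the same 30-person pilot; with 1.2 at follow-up, power at 0.38% is about 77%, not 90%.

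*Protocol*

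**What the plan says.** Protocol 11.3 (Sample Size) first gives the reason for the number randomized: "The sample size of 330 randomized participants was selected to provide sufficient exposure to the AID system for regulatory purposes". It then describes the power of that sample for the primary endpoint, 13-week HbA1c adjusted for baseline. The source of the variability is stated: "HbA1c data from N=30 participants in the 2IQ pilot study were used to estimate the SD for the power calculation". The value follows: "The SD for baseline values was 1.0" (per cent). The other inputs are "Assuming a similar SD at follow-up, correlation of 0.3 with baseline, and a two-sided test with type 1 error at 5" (per cent). The result is that "N=300 completers will be able to detect an HbA1c difference as small as 0.38% with 90% power", with 85% power at 0.35% and 80% at 0.33%. SAP 4 repeats the same inputs and results.

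Protocol 1.3 describes the earlier study that led to this trial. It begins "A prospective single-arm 6-week trial, conducted to provide preliminary data on the safety and" glycemic outcomes, and it gives the cohort of thirty adults as "T2D (mean age 54±12 years, mean HbA1c 8.6±1.2, median BMI 31) using either MDI (N=15"), with the remainder on a pump or on basal insulin without bolus. Protocol 1.4 then justifies the present trial by the "promising results from the preliminary study evaluating Control-IQ in T2D, a larger trial with a" randomized design being needed.

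**The concern.** Both passages appear to describe the same 30 people, yet one gives an HbA1c SD of 1.0 and the other 1.2. The number of participants, the device and the disease all match, and neither document mentions another Control-IQ pilot of 30 people with type 2 diabetes. Section 1.3 does not use the name 2IQ, so the match is an inference, though a strong one.

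The plan's power rests on the smaller value. By assuming a similar SD at follow-up, the plan carries the baseline figure straight into the variance of the primary outcome. If the larger value is correct, all three detectable differences are too favourable. HbA1c is also the first test in the fixed sequence (Protocol 11.13, SAP 16), so a miss on it ends formal testing of every CGM endpoint below it. Anyone interpreting a null or borderline result would turn to these power figures.

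**Working it through.** **Inputs**
- SD 1.0, follow-up SD similar to baseline, r = 0.3, two-sided 5%, 300 completers: Protocol 11.3 and SAP 4.
- Allocation 2:1, so 200 AID and 100 Control: Protocol Summary (Treatment Groups) and Protocol 4.3.
- Alternative SD 1.2: Protocol 1.3.

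**Reading of ±1.2.** The ± is not labelled. A standard error of 1.2 with n = 30 would imply an SD of 1.2 × √30 ≈ 6.6 HbA1c points, which is not credible. Age is reported in the same form (54±12). It is therefore read as an SD. Rounding cannot turn 1.2 into 1.0. A subset does not readily explain the gap either, because 11.3 says N=30 and 1.3 says thirty adults.

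**Formulas** (normal approximation, baseline-adjusted comparison)
- SE = SD at follow-up × √(1 − r²) × √(1/200 + 1/100)
- Power = Φ(difference/SE − 1.96)
- Detectable difference = (1.96 + z for the power) × SE, with z = 1.282, 1.036 and 0.842 for 90%, 85% and 80%

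**Plan's own figures, SD 1.0**
- SE = 1.0 × 0.9539 × 0.12247 = 0.1168
- Power at 0.38 / 0.35 / 0.33 = 90.2% / 85.0% / 80.6%
- Detectable difference at 90 / 85 / 80% power = 0.379 / 0.350 / 0.327

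These agree with the stated figures, so the calculation is correct for its input.

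**Same calculation, SD 1.2**
- SE = 1.2 × 0.9539 × 0.12247 = 0.1402
- Power at 0.38: 0.38/0.1402 − 1.96 = 0.75, giving 77%. At 0.35 and 0.33 it is 70% and 65%.
- Detectable difference at 90 / 85 / 80% power = 0.454 / 0.420 / 0.393

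A noncentral t with 297 df gives 77.1% at 0.38. Applying 10% drop-out literally (198 versus 99) gives 89.9% with SD 1.0 and 76.9% with SD 1.2.

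**Sensitivity of power at 0.38%**

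| SD 1.2, by r | r = 0 | 0.3 | 0.4 | 0.5 | 0.6 |
|---|---|---|---|---|---|
| Power | 73% | 77% | 81% | 85% | 90% |

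| r = 0.3, by follow-up SD | 1.0 | 1.05 | 1.1 | 1.15 | 1.2 |
|---|---|---|---|---|---|
| Power | 90% | 87% | 84% | 81% | 77% |

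With SD 1.2, the correlation that recovers the stated power solves 1.44 × (1 − r²) = 0.91, so r = √(1 − 0.91/1.44) = 0.61, about twice the assumed 0.3. The baseline SD does not enter the formula itself: if it is 1.2 but the follow-up SD is 1.0, power stays at about 90%.

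**The case against.** The contradiction is inferred. Section 1.3 does not name the pilot and gives no time point or assay for its HbA1c value. One study can take two pre-treatment HbA1c measurements. The present trial does: a point-of-care or local value at screening and a central-laboratory value at randomization. If the pilot did the same, both SDs could be correct. This stands as a possibility, but the documents do not say it, and saying it would be one way to resolve the point.

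The 77% is also conditional. It needs 1.2 to be the right SD, to persist to 13 weeks, and r to stay at 0.3. This is true. The first table spans 73% to 90%, and 77% is the value under the plan's own r and its own assumption of an unchanged SD.

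An SD of 1.0 from 30 people has a 95% interval of about 0.80 to 1.34 (chi-square, 29 df, normality assumed), which contains 1.2. This shows how imprecise the input is. It does not explain two different SDs from the same 30 people.

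Finally, nothing in the design depends on the figure. The number randomized was set by exposure, and none of the three differences is named as a target or as clinically important. The primary model estimates its variances from the trial data, so neither pilot SD touches the estimate, its confidence interval or the type 1 error. All of this stands. It limits the consequence to the power statement, but the documents still make three specific power claims on an input that they contradict elsewhere.

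**Conclusion.** The concern holds. The stated power is computed correctly from an SD of 1.0, but Protocol 1.3 gives 1.2 for what appears to be the same pilot, and neither document reconciles the two. If 1.2 is right and holds at follow-up with r = 0.3, the type 2 error at 0.38% is about 23% instead of 10%, and the difference detectable with 90% power is 0.45% instead of 0.38%. This rests on the two descriptions being of one pilot, on reading ± as an SD, and on the plan's own follow-up assumptions. It is an inconsistent input, not a calculation error, and it does not show that the trial is too small.

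**What to change.** Check the pilot data and establish which HbA1c measurements gave each SD.

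- If 1.2 is correct, restate Protocol 11.3 and SAP 4 as 0.45%, 0.42% and 0.39% at 90%, 85% and 80% power, or equivalently about 77% power at 0.38%.
- If 1.0 is correct, correct the value in section 1.3. If both are correct for different measurements, say in 11.3 which values gave 1.0.
- If the pilot's follow-up SD and its correlation with baseline are available, cite them beside the assumed values, since these are what determine power.

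The cost is a look at existing pilot data, then either one corrected or explained value or one rewritten paragraph in each document. The sample size, endpoint, model, alpha and testing order do not change.

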11.5.2 Other Sensitivity Analyses

1404 Confounding

1403

1420

1424

1425

1426

- 1405 A sensitivity analysis will also be conducted if potential confounding factors collected at
- baseline are detected.
- 1407 The imbalance will be assessed based on clinical judgment reviewing the distributions in the two
- treatment arms, not on a p-value. The person making this judgement will be unaware of whether
- there is an association between baseline variables and study outcome. All variables obtained on a
- 1410 continuous scale will be entered into the models as continuous variables, unless it is determined
- that a variable does not have a linear relationship with the outcome. In such a case,
- categorization and/or transformation will be explored.

1413 Missing Data

- 1414 Missing data will be handled using direct likelihood method for the primary analysis. It is worth
- noting that all statistical methods for handling missing data rely on untestable assumptions and
- there is no one correct way to handle missing data. Our goal is to minimize the amount of
- missing data so that the results will not be sensitive to which statistical method is used.
- To that end, sensitivity analyses will be performed to explore whether results are similar for
- primary analysis when using different methods. The following methods will be applied:
 - Rubin's multiple imputation with treatment group in the imputation model
- Available cases only
- Multiple imputation with pattern mixture model assuming the dropout trajectory of the AID group was that of the Control group (Mallinckrodt and Clark, 2003)
 - Tipping point analysis to determine the magnitude of selective dropout bias necessary to alter conclusions of the study.

11.6 Analysis of the Primary Efficacy Endpoint: HbA1c

- HbA1c at 13 weeks will be compared between the AID and Control Groups using a linear mixed
- effects regression model adjusting for baseline HbA1c and clinical center (random factor). A
- separate variance will be modelled for each treatment group. HbA1c is expected to be normally
- distributed, but regression diagnostics will be performed to check the residuals and an
- appropriate alternative transformation or robust statistical method (e.g., non-parametric or MM
- estimation) will be performed if the residuals have a skewed distribution. In the event that some
- 1433 HbA1c values are not available at 13 weeks, then the linear mixed effect regression model will
- 1434 use the method of direct likelihood to incorporate information from baseline measurements to
- calculate the maximum likelihood at 13 weeks. Only central lab HbA1c measurements will be
- used in the analyses. Imbalances between groups in important covariates are not expected to be
- of sufficient magnitude to produce confounding. However, the presence of confounding will be
- of sufficient magnitude to produce combanding. However, the presence of combanding will be
- evaluated in the sensitivity analyses by including factors potentially associated with the outcome
- 1439 for which there is an imbalance between groups (11.5.2).

1440	11.7 Analysis of Secondary Endpoints
1441	11.7.1 CGM Metrics
1442 1443 1444	Baseline values for each CGM metric will be computed from 14 days of CGM data prior to randomization. A minimum of 72 hours of CGM data will be required to calculate baseline metrics.
1445 1446	CGM data starting from randomization visit through the 13-week visit will be included in the calculation of each CGM metric for each participant, giving equal weight to each CGM point.
1447 1448 1449 1450 1451	Calculation of CGM metrics for the treatment group comparisons will exclude the challenges and the period through 6 AM on the day following the end of the challenge. CGM metrics during and following the challenges will be reported separately as described in section 11.15.3 and an overall analysis within the AID group will be performed for all CGM data including the challenge data as described in section 11.15.2.
1452 1453 1454 1455 1456 1457 1458 1459	CGM-measured prolonged hyperglycemia events are defined as ≥90 cumulative minutes with CGM glucose >300 mg/dL within a 120-minute period (the participant becomes eligible for another prolonged hyperglycemia event after the CGM glucose is <180 mg/dL for ≥15 consecutive minutes). CGM-measured hypoglycemia events are defined as ≥15 consecutive minutes with CGM glucose <54 mg/dL (the participant becomes eligible for another hypoglycemia event after the CGM glucose is ≥70 mg/dL for ≥15 consecutive minutes). For each of these metrics, the number of events per week is calculated for each participant and each metric is then analyzed as a continuous variable as described below.
1460 1461 1462 1463 1464 1465 1466 1467	Summary statistics (mean \pm SD or median (quartiles)) will be reported for the CGM-measured metrics at baseline and during follow up as well as for differences from baseline by treatment group. CGM metric differences between AID and Control Groups will be compared using a linear mixed effects regression model adjusting for the baseline value of the metric and clinical center (random effect). A separate variance will be modelled for each group. Residual values will be examined for an approximate normal distribution. If residuals are highly skewed, then a transformation or robust statistical method (e.g., non-parametric or MM estimation) will be used instead. Missing data will be handled using direct likelihood.
1468	11.7.2 Binary Outcomes
1469 1470 1471 1472	For the binary HbA1c outcomes, risk-adjusted percentages by treatment group will be computed at 13 weeks from a logistic regression model. The logistic regression will adjust for baseline HbA1c (as a continuous factor) and clinical site using generalized estimating equations (GEE). Similar analyses will be done for the binary CGM outcomes.
1473	11.8 Questionnaires and Other Outcomes Analyses
1474 1475 1476 1477	For questionnaires administered to both randomization groups, comparisons will be made using similar linear models as described above for the primary and key secondary outcomes. If questionnaires include a total score, separate models will be run for the total score and selected subscales.
1478 1479	Similarly, for insulin, weight and BMI metrics comparisons will be made using similar linear models as described above for the primary HbA1c analysis.

1480	11.9 Safety Analyses
1481 1482 1483	All randomized participants will be included in the safety analyses and all of their post-randomization safety events will be reported. Separately, any adverse events occurring between screening and randomization will be reported.
1484 1485 1486 1487 1488	All reportable adverse events will be tabulated by treatment group. Details will be provided in a listing of each event, including Medical Dictionary for Regulatory Activities (MedDRA) term and MedDRA System Organ Class. Safety analyses for the RCT will include events occurring on or after randomization until and including the 13-week visit or Day 98 from randomization, whichever occurs first.
1489 1490 1491 1492	Formal statistical testing only will be performed for selected safety endpoints. For the following outcomes, mean \pm SD or summary statistics appropriate to the distribution will be tabulated by treatment group and formal statistical comparisons will be performed if there are enough events (at least 5 events combined between the two treatment groups):
1493 1494 1495 1496	 Number of SH events and SH event rate per 100 person-years Number of DKA events and DKA event rate per 100 person-years Number of hyperosmolar hyperglycemic syndrome events and rate per 100 person-years Other serious adverse events
1497 1498 1499	If enough events occur for the severe hypoglycemia and DKA outcomes and other serious adverse events, the numbers of events will be compared between the two treatment groups during the RCT using a robust Poisson regression as detailed in the SAP.
1500	11.9.1 Safety Tabulations Specific to the AID Group
1501	For the AID Group, all of the following will be tabulated:
1502 1503 1504	 Adverse device effects (ADE) Serious adverse device events (SADE) Unanticipated adverse device effects (UADE)
1505	11.10 Additional Tabulations and Analyses
1506	The following tabulations will be performed according to treatment group:
1507 1508 1509 1510 1511 1512 1513	 Baseline demographics and clinical characteristics A flow chart accounting for all participants for all visits Visit completion rates for each follow-up visit Protocol deviations Modifications in non-insulin diabetes drugs during the study Number and reasons for unscheduled visits and phone calls Amount of CGM data during the 13 weeks of the study
1514	11.11 Planned Interim Analyses
1515 1516 1517	No formal interim efficacy analyses are planned. The DSMB will review safety data at intervals, with no formal stopping rules other than the guidelines provided in the participant-level and study-level stopping criteria (as defined in Section 9.6.2).

1518	11.12 Subgroup Analyses
1519 1520 1521	In exploratory analyses, the primary outcome (HbA1c) and time in range 70-180 mg/dL will be compared in baseline subgroups. Treatment group by subgroup factor interaction terms will be added to the linear models described above.
1522 1523 1524 1525 1526 1527	Formal tests will be done only if the overall result is statistically significant. Results will be tabulated by subgroups regardless of statistical significance. For continuous variables, results will be displayed in subgroups based on cutpoints although the analysis will utilize the variable as continuous. If there is insufficient sample size in a given subgroup, the cutpoints for continuous measures may be adjusted per the observed distribution of values. Cutpoint selection for display purposes will be made masked to the outcome data.
1528	Subgroups will be analyzed according to the following baseline factors:
1529 1530 1531 1532 1533 1534 1535 1536 1537 1538 1539 1540	 Baseline HbA1c Baseline time in range 70-180 mg/dL Diabetic medication use Body mass index Total daily insulin (<100 units versus ≥100 units) Sex Age (>50 years old versus ≤50 years old—assuming sufficient numbers in each category) Race/Ethnicity Scores on the Subjective Numeracy Survey C-peptide level Additional subgroups to be defined in the SAP
1541	11.13 Multiple Comparison/Multiplicity
1542	Hierarchical Analyses
1543 1544 1545 1546 1547 1548 1549	To preserve the overall type 1 error for the primary endpoint and key secondary endpoints as listed in section 11.4.2, a hierarchical testing procedure will be used. If the primary analysis for HbA1c results in a statistically significant result ($p < 0.05$), then testing at the 0.05 level will proceed to the next outcome metric. This process continues iteratively moving to the next variable down on the list until a non-significant result is observed, or all 10 variables have been tested. If a non-significant result is encountered, then formal statistical hypothesis testing is terminated and any variables lower on the list will not be formally tested.
1550 1551 1552 1553 1554 1555	Regardless of the results of the hierarchical testing, summary statistics appropriate to the distribution will be tabulated by treatment group for each hierarchical outcome. A 95% confidence interval for the treatment group difference also will be calculated for all hierarchical outcomes listed above. However, a confidence interval that excludes zero will not be considered a statistically significant result if an outcome variable higher on the hierarchical list failed to reach statistical significance.
1556	All Other Secondary Analyses
1557 1558	For the other secondary analyses, the false discovery rate will be controlled using the adaptive Benjamini-Hochberg procedure.

1559 1560	P-values from safety analyses, sensitivity analyses, and per-protocol analyses will not be adjusted for multiple comparisons.
1561	11.14 Exploratory Treatment Group Comparisons
1562	The following additional treatment group comparisons will be performed:
1563	 Separate CGM analyses for daytime and nighttime
1564 1565 1566 1567 1568 1569	 Separate sub-analyses for participants negative for GAD antibodies (if GAD antibodies are present in ≥5% of participants) Efficacy and safety outcomes in participants using an SGLT2 inhibitor Efficacy and safety outcomes in participants using a GLP-1 receptor agonist Efficacy and safety outcomes in participants with TDI ≥100 units, ≥ 150 units, ≥ 200 units. These may include subgroup analyses.
1570	11.15 Additional Analyses and Tabulations for the Single-Arm AID Group
1571	11.15.1 Tabulations Specific to the AID Group
1572	The following tabulations will be made for the AID group
1573 1574 1575 1576 1577 1578 1579	 Number of participants who stopped AID use and reasons % time in closed loop Occlusion events that occur while using the AID system Reportable device malfunctions and other reported device issues Frequency of use of sleep mode and exploratory outcomes for times with versus without sleep mode Frequency of use of exercise mode
1580	11.15.2 Analyses of Complete CGM Data Set
1581 1582 1583 1584	CGM metrics will computed over the entire 13 weeks of the trial (including the challenge periods) and compared with the baseline CGM metrics using paired t-tests or nonparametric approaches depending on the distribution of the data. Binary outcomes will be assessed using McNemar's test.
1585	11.15.3 Analysis of Data from Meal and Exercise Challenges
1586 1587 1588 1589 1590	The number of each challenge per participant will be tabulated. Any adverse events occurring during these challenges will be reported by type of challenge in addition to their being included in the overall safety analyses. Selected CGM metrics for hypoglycemia and hyperglycemia will be computed for each challenge and reported as summary statistics for the time period during and until 6 AM on the day following each challenge.

1591	Chapter 12: Data Collection and Monitoring
1592	12.1 Case Report Forms and Other Data Collection
1593 1594 1595 1596 1597 1598 1599 1600	The main study data are collected on electronic case report forms (CRFs). When data are directly collected in electronic case report forms, this will be considered the source data. For any data points for which the eCRF is not considered source (e.g. lab results that are transcribed from a printed report into the eCRF), the original source documentation must be maintained in the participant's study chart or medical record. This source must be readily verifiable against the values entered into eCRF. Even where all study data are directly entered into the eCRFs at office visits, evidence of interaction with a live subject must be recorded (e.g., office note, visit record, etc.)
1601 1602	Electronic device data files are obtained from the study software and individual hardware components. These electronic device files are considered the primary source documentation.
1603	12.2 Study Records Retention
1604 1605 1606	Each participating site will maintain appropriate medical and research records for this trial, in compliance with ICH E6 and regulatory and institutional requirements for the protection of confidentiality of participants.
1607 1608 1609 1610 1611 1612 1613	Study documents should be retained for a minimum of 2 years after the last approval of a marketing application in an ICH region and until there are no pending or contemplated marketing applications in an ICH region or until at least 2 years have elapsed since the formal discontinuation of clinical development of the investigational product. These documents should be retained for a longer period, however, if required by local regulations. No records will be destroyed without the written consent of the sponsor, if applicable. It is the responsibility of the sponsor to inform the investigator when these documents no longer need to be retained.
1614	12.3 Quality Assurance and Monitoring
1615 1616 1617 1618 1619 1620	Designated personnel from the Coordinating Center will be responsible for maintaining quality assurance (QA) and quality control (QC) systems to ensure that the clinical portion of the trial is conducted and data are generated, documented and reported in compliance with the protocol, Good Clinical Practice (GCP) and the applicable regulatory requirements, as well as to ensure that the rights and wellbeing of trial participants are protected and that the reported trial data are accurate, complete, and verifiable. Adverse events will be prioritized for monitoring.
1621 1622 1623 1624 1625 1626	A risk-based monitoring (RBM) plan will be developed and revised as needed during the course of the study, consistent with the FDA "Guidance for Industry Oversight of Clinical Investigations — A Risk-Based Approach to Monitoring" (August 2013). Study conduct and monitoring will conform with 21 Code of Federal Regulations (CFR) 812. This plan describes in detail who will conduct the monitoring, at what frequency monitoring will be done, at what level of detail monitoring will be performed, and the distribution of monitoring reports.
1627 1628 1629 1630	The data of most importance for monitoring at the site are participant eligibility and adverse events. Therefore, the RBM plan will focus on these areas. As much as possible, remote monitoring will be performed in real-time with on-site monitoring performed to evaluate the verity and completeness of the key site data. Elements of the RBM may include:

1631 Qualification assessment, training, and certification for sites and site personnel 1632 • Oversight of Institutional Review Board (IRB) coverage and informed consent procedures 1633 1634 • Central (remote) data monitoring: validation of data entry, data edits/audit trail, protocol review of entered data and edits, statistical monitoring, study closeout 1635 • On-site monitoring (site visits): source data verification, site visit report 1636 • Agent/Device accountability 1637 1638 • Communications with site staff 1639 • Patient retention and visit completion 1640 • Quality control reports • Management of noncompliance 1641 1642 • Documenting monitoring activities 1643 • Adverse event reporting and monitoring 1644 Coordinating Center representatives or their designees may visit the study facilities at any time in order to maintain current and personal knowledge of the study through review of the records, 1645 comparison with source documents, observation and discussion of the conduct and progress of 1646 the study. The investigational site will provide direct access to all trial related sites, source 1647 1648 data/documents, and reports for the purpose of monitoring and auditing by the sponsor, and 1649 inspection by local and regulatory authorities. 1650 12.4 Protocol Deviations 1651 A protocol deviation is any noncompliance with federal regulation, the clinical trial protocol, 1652 GCP, IRB requirements, or procedure requirements. The noncompliance may be either on the 1653 part of the participant, the investigator, or the study site staff. A significant (or major) deviation is any deviation that departs from the established materials in such a way that it poses an increase 1654 1655 in the risk to subjects, adversely affects the welfare, rights, or safety of the research subjects, or 1656 negatively influences the scientific study integrity. As a result of a significant deviation, a corrective and preventive action plan shall be developed by the site and implemented promptly. 1657 1658 The site PI/study staff is responsible for knowing and adhering to all applicable IRB

requirements. Further details about the handling of protocol deviations will be included in the

1659

1660

monitoring plan.

1661	Chapter 13: Ethics/Protection of Human Participants
1662	13.1 Ethical Standard
1663 1664 1665	The investigator will ensure that this study is conducted in full conformity with Regulations for the Protection of Human Participants of Research codified in 45 CFR Part 46, 21 CFR Part 50, 21 CFR Part 56, and/or the ICH E6.
1666	13.2 Institutional Review Boards
1667 1668 1669 1670 1671 1672	The protocol, informed consent form(s), recruitment materials, and all participant materials will be submitted to the IRB for review and approval. Approval of both the protocol and the consent form must be obtained before any participant is enrolled. Any amendment to the protocol will require review and approval by the IRB before the changes are implemented to the study. All changes to the consent form will be IRB approved; a determination will be made regarding whether previously consented participants need to be re-consented.
1673	13.3 Informed Consent Process
1674	13.3.1 Consent Procedures and Documentation
1675 1676 1677 1678 1679 1680 1681 1682 1683 1684	Informed consent is a process that is initiated prior to the individual's agreeing to participate in the study and continues throughout the individual's study participation. The consent process may be done electronically and virtually, if approved by the IRB. Extensive discussion of risks and possible benefits of participation will be provided to the participants. Consent forms will be IRB-approved and the participant will be asked to read and review the document. The investigator will explain the research study to the participant and answer any questions that may arise. All participants will receive a verbal explanation in terms suited to their comprehension of the purposes, procedures, and potential risks of the study and of their rights as research participants. Participants will have the opportunity to carefully review the consent form and ask questions prior to signing.
1685 1686 1687	The participants should have the opportunity to discuss the study with their surrogates or think about it prior to agreeing to participate. The participant will sign the informed consent document prior to any procedures being done specifically for the study.
